1. PURPOSE OF THE STUDY

a. Brief Summary

The purpose of this study is to determine if intravenous fosaprepitant can interfere with nervous system monitoring signals in patients having surgery under general anesthesia. Fosaprepitant is a drug commonly used to prevent post-operative nausea and vomiting, and works by inhibiting "substance P", which is found in the brain and spinal cord. Theoretically, fosaprepitant could interfere with nervous system recordings because of its effect on substance P, but it is not known if this actually occurs. The drug will be given after the patient has been anesthetized but before surgical incision so that if there are any changes on the intraoperative neuromonitoring signals they can only be attributed to fosaprepitant.

b. Objectives

If fosaprepitant alters intraoperative neuromonitoring signals during surgical procedures under general anesthesia, it would be important because anesthesiologist's who administer this drug would want to give it at the beginning of surgery when changes in intraoperative neuromonitoring signals would be unlikely to mean that these changes were due to surgical damage to the nervous system.

c. Rationale for Research in Humans

We are specifically interested in evaluating if fosaprepitant alters intraoperative neuromonitoring signals in human patients having surgery under general anesthesia.

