2. STUDY PROCEDURES

a. Procedures

On the day of surgery the patient will be consented in the preoperative area. We regularly use fosaprepitant in surgical patients undergoing procedures under general anesthesia with intraoperative neuromonitoring.

The patient will receive a single dose of 150 mg intravenous fosaprepitant after general anesthesia has been induced as prepared by pharmacy. Intraoperative neuromonitoring signals will be monitored for any changes during and after the administration of fosaprepitant.

The patient's intraoperative anesthetic management will be that typically utilized for surgical procedures with intraoperative neuromonitoring.

b. Procedure Risks

Using fosaprepitant in the operating room is widely used in the United States and is generally considered safe. This study will no withhold medication used to treat post-operative nausea and vomiting, rather, it seeks to determine if utilizing this very safe and effective medication during surgical procedures under general anesthesia with intraoperative neuromonitoring will alter or change intraoperative neuromonitoring signals due to the mechanism of action of the drug.

c. Use of Deception in the Study

No deception will be used.

d. Use of Audio and Video Recordings

No audio or video will be recorded.

e. Alternative Procedures or Courses of Treatment

At this point the use of fosaprepitant during surgery is at the discretion of the anesthesiologist. The effect of this medication on intraoperative neuromonitoring signals in patients having surgery under general anesthesia is not understood. No standard treatment is being withheld.

f. Will it be possible to continue the more (most) appropriate therapy for the participant(s) after the conclusion of the study?

After surgery the primary surgery team is free to utilize any nausea and vomiting control scheme they would like to use.

g. Study Endpoint(s)

Our study endpoint is whether a single dose of fosaprepitant at the start of surgery in patients having surgery under general anesthesia with intraoperative neuromonitoring causes any change in intraoperative neuromonitoring signals, and to quantify any such changes.

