3. BACKGROUND

a. Past Experimental and/or Clinical Findings

Fosaprepitant is a very effective medication used to prevent post-operative nausea and vomiting in patients having surgery under general anesthesia. The mechanism of action

of this medication is through substance P inhibition, which has effects on numerous sensory systems in the brain and spinal column. In patients who have surgery under general anesthesia with intraoperative neuromonitoring, the sensory and motor pathways are monitored throughout the surgical procedure. It is not known if fosaprepitant could interfere with these intraoperative neuromonitoring signals due to its effect on sensory pathways via substance P inhibition.

b. Findings from Past Animal Experiments

No relevant animal literature exists.

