8. PARTICIPANT POPULATION

a. Planned Enrollment

The total number of participants expected to enroll is 50.

Patients presenting for surgery under general anesthesia with intraoperative neuromonitoring will be approached to participant in this study.

All participants will be at Stanford University Medical Center.

We selected this patient population because we are particularly interested in knowing what effects, if any, fosaprepitant has on intraoperative neuromonitoring signals in patients having surgery under general anesthesia.

b. Age, Gender, and Ethnic Background

There are no exclusions or preferences based on age, gender, or ethnic background.

c. Vulnerable Populations

We are not specifically seeking out any potentially vulnerable populations.

d. Rationale for Exclusion of Certain Populations

No children will be enrolled because this study will be carried out at Stanford University Medical Center which only manages adult patients.

e. Stanford Populations

Enrollment of laboratory personnel, employees, and/or students would be purely coincidental. No payment will be provided for participation.

f. Healthy Volunteers

No healthy volunteers will be enrolled in this study. Only patients coming to Stanford University Medical Center for surgery requiring general anesthesia and intraoperative neuromonitoring will be approached to participate.

g. Recruitment Details

Patients coming to Stanford University Medical Center for surgery requiring general anesthesia and intraoperative neuromonitoring will be approached to participate.

h. Eligibility Criteria**i. Inclusion Criteria**

Patients presenting to Stanford University Medical Center for surgery requiring general anesthesia with intraoperative neuromonitoring will be approached to participate.

ii. Exclusion Criteria

Exclusion criteria include patient refusal or inability to consent to this study, or a contraindication to receiving fosaprepitant.

i. Screening Procedures

Medical chart reviewed by the anesthesiologists involved in the study.

j. Participation in Multiple Protocols

Patients will be asked about participation in other studies. Enrollment in other studies that don't interfere with this study is acceptable. Surgical patients are frequently asked by the surgeon to allow the collection of tissue samples for research purposes. This is done during surgery and does not in any way interfere with this study.

k. Payments to Participants

Subjects will not receive payment.

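### Section 1.a claims that dosing before incision makes any signal change attributable only to fosaprepitant; this excludes surgical causes only for signals also read before incision, and even there anesthetic or time-related change remains possible

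*Protocol*

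**What the plan says.** Section 1.a of the protocol fixes the timing of the dose and draws its conclusion in one sentence: the drug is given once the patient is under anesthesia and "before surgical incision so that if there are any changes on the intraoperative neuromonitoring signals they can only be attributed to fosaprepitant". It gives no period over which the signals are to be read.

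Section 2.a places the dose after induction without mentioning incision. On measurement it says: "Intraoperative neuromonitoring signals will be monitored for any changes during and after the administration of fosaprepitant". No end to that period is given. The same section leaves anesthetic management to what is usual for monitored surgery.

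Section 2.g places the dose at the start of surgery and makes the endpoint whether it "causes any change in intraoperative neuromonitoring signals, and to quantify any such changes". It does not say over what period, or how cause is to be judged.

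Section 3.a notes that in such patients "the sensory and motor pathways are monitored throughout the surgical procedure". Sections 2.a and 8 describe one group of patients, all dosed; no untreated or placebo group appears.

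**The concern.** The timing of the dose and the timing of the reading are separate matters. Section 1.a fixes the first and draws a conclusion that also depends on the second. Once the operation has begun, an earlier dose does nothing to exclude surgery as the cause of a later change.

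This matters more here than in a controlled study. With every participant dosed and no comparator described, the case for a drug effect rests on the change within each patient over time and on the argument in 1.a. If that argument is carried over to recordings made after incision, changes caused by surgery would be read as drug effects. If it is confined to the time before incision, surgery drops out as a cause, but drift after induction, whether anesthetic or simply with time, does not.

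**Working it through.** No arithmetic applies. The protocol gives no figure for how often signals change during surgery, no threshold for a change, and no definition of a participant who counts as having one. The planned enrollment of 50 (section 8.a) does not bear on the logic. The check is to set the sections side by side and ask, for each period, which causes of a signal change the design excludes.

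**The conclusion in 1.a.** It covers any change and names one permitted cause. For it to hold, every other cause must be excluded over every period in which signals are read.

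**The periods that the protocol admits.** Section 2.a starts the watch with the infusion and gives it no end. Section 2.g sets no window. Section 3.a shows that recordings will exist for the whole operation. Nothing in the protocol limits the endpoint to readings before incision.

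**Causes, period by period.**

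| Period of reading | Surgical cause excluded? | Anesthetic or time-related cause excluded? | Does 1.a hold? |
|---|---|---|---|
| Dose to incision | Yes, since surgery has not begun | No: no comparator, and anesthetic management follows usual practice | No, though surgery is removed |
| After incision | No | No | No |

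**Whether the protocol recognises surgery as a rival cause.** It does. Section 1.b considers when clinicians would choose to dose if the drug proves to alter signals, and says of an early dose that "changes in intraoperative neuromonitoring signals would be unlikely to mean that these changes were due to surgical damage to the nervous system". Section 10 is concerned with drug-related changes being mistaken for surgical damage. The confusion can run in the other direction as well, and 1.a does not allow for that.

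**What follows.** The reason given in 1.a supports a narrower statement: signals read between dose and incision are free of surgical causes. It does not support sole attribution to the drug in either period. The narrower statement also depends on a reading limit that appears in neither 2.a nor 2.g.

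**The case against.** The strongest reply is that 1.a should be read in context. The sentence explains why the drug is given before incision, and its natural sense is that changes seen around the dose, before surgery starts, are not surgical. On that reading 2.a and 2.g are silent on the window and do not contradict 1.a. Endpoint windows, baselines and the handling of later recordings are commonly settled in a statistical analysis plan, which may exist and is not shown. Section 3.a is background on routine monitoring, and 1.b concerns when clinicians would choose to give the drug; neither is an attribution rule for the study.

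Much of this stands. The intent behind 1.a probably was a pre-incision reading. The absence of a detailed window is not in itself a fault of the protocol. Section 3.a shows only that later recordings will exist, and 1.b shows only that the protocol knows surgery can change signals.

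The reply does not rescue the sentence. Sole attribution is stated in the protocol, and it is too strong even on the sympathetic reading, because drift after induction is not excluded. The baseline recording and the infusion and incision times also have to be captured at the time of surgery; an analysis plan cannot supply them afterwards if they were not noted.

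A reader might infer that the study will count post-incision changes as drug effects, and that its result is therefore biased. The documents do not support that: no section says that such changes are counted. Nor do they support a projected number of misattributed participants, because the protocol defines no responder proportion and any rate of surgical change would be invented.

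**Conclusion.** The attribution statement in 1.a is wrong as written and should be corrected. Dosing before incision removes surgical causes only from signals also read before incision, and even those cannot be credited to the drug alone without a comparator.

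The size of any resulting error cannot be derived from the documents. It is near zero, as regards surgical causes, if the pre-incision reading implied by 1.a is followed. If 1.a is applied to the open window of 2.a, surgical changes would be credited to the drug, to an unknown extent. Anesthetic or time-related change remains possible in both cases.

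This rests on two readings of the text: that no comparator exists, since none is described, and that no other section restricts the reading period, since none was found. The correction is worth making before data are collected, but it is not evidence that the study's conclusions will be wrong. A reader might also infer that a change confined to the pre-incision period would prove a drug effect; that does not follow either, for the reason just given.

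**What to change.** - **Sections 2.a and 2.g:** base the primary drug-attribution reading on the change from a post-induction, pre-dose baseline to recordings made before incision. Note infusion and incision times against the recordings. The three descriptions of dose timing (before incision in 1.a, after induction in 2.a, start of surgery in 2.g) should be reconciled at the same time, so that the reading window is well defined.
- **Later recordings:** report post-incision recordings descriptively, without attribution to the drug.
- **Section 1.a:** replace the sole-attribution wording with a statement that reading the signals before incision removes surgical causes, and that anesthetic or time-related change remains possible because there is no control group.

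The cost is a change of wording, one baseline recording and two noted times per patient. The real drawback is that drug effects which first appear after incision become exploratory. The protocol gives no interval between dose and incision, so the window will vary between patients and may be short in some. Its length should be reported.

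### Section 1.a attributes any signal change to fosaprepitant alone, but dosing before incision only makes surgical injury unlikely, and only for readings taken before incision

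*Protocol*

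**What the plan says.** - Section 1.a places the dose after anesthesia and before incision, and concludes that "if there are any changes on the intraoperative neuromonitoring signals they can only be attributed to fosaprepitant".
- Section 1.b gives a more cautious version of the same rationale: changes seen early "would be unlikely to mean that these changes were due to surgical damage to the nervous system".
- Section 2.a gives the drug to the patient "after general anesthesia has been induced". No comparator or drug-free group is described. On observation it says: "Intraoperative neuromonitoring signals will be monitored for any changes during and after the administration of fosaprepitant". It sets no end to that period at incision.
- Section 2.a also says that "intraoperative anesthetic management will be that typically utilized for surgical procedures with intraoperative neuromonitoring". It does not say that conditions are held steady around the dose.
- Section 2.g frames the endpoint causally, as whether "a single dose of fosaprepitant at the start of surgery" brings about any change in the signals, and adds that such changes will be quantified.
- Section 8.a plans 50 participants. Section 8.h admits any surgery that needs general anesthesia with neuromonitoring.

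**The concern.** Giving the drug before incision removes the surgeon's work as an explanation for what is seen before incision. It does nothing about causes that run alongside the dose: time passing since induction, adjustments to the anesthetic, and the normal scatter of the recordings. Without a comparison that carries the same causes but not the drug, a change after the dose could be any of these, and one of them could also hide a real drug effect.

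What is at stake is the conclusion. Section 10 says that a positive finding would guide when in an operation the drug is avoided. If the sentence in 1.a is taken over into the report, either a change or the absence of one will be read as more than the design shows.

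**Working it through.** **Which explanations the design excludes.** The protocol states no figure to reproduce here, since 50 is an enrollment count without a calculation. So the main check sets the claim in 1.a against the procedures in 2.a.

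| Explanation for a change after the dose | Reading before incision | Reading after incision |
|---|---|---|
| Surgical injury | made unlikely (1.b) | not excluded |
| Time since induction | not excluded | not excluded |
| Changing anesthetic conditions (usual management, 2.a) | not excluded | not excluded |
| Ordinary signal variability | not excluded | not excluded |

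For 1.a to be true, every row would have to be excluded in every column that the observation period covers. One cell of eight is addressed, and 1.b calls that one unlikely rather than impossible. The right-hand column is in play because 2.a does not close the period at incision.

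**Illustration of size, on assumed inputs.** The protocol gives no drift, SD, test or threshold. Assume n = 50 (8.a), a two-sided 5% paired t-test on mean within-patient change, no drug effect, and a mean non-drug drift of d standard deviations of that change.

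The chance of declaring a change is P(|T| > t(0.975, 49)), where T is noncentral t with 49 degrees of freedom and noncentrality d × √50 = 7.071 d.

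| Assumed drift d (SD) | Noncentrality | Chance of declaring a change |
|---|---|---|
| 0 | 0 | 0.050 |
| 0.1 | 0.707 | 0.107 |
| 0.2 | 1.414 | 0.284 |
| 0.3 | 2.121 | 0.548 |

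A normal approximation, Φ(d√50 − 1.96) + Φ(−d√50 − 1.96), gives 0.109, 0.293 and 0.564 for the last three rows, so the result does not depend on the choice of test.

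**Masking.** With a true drug effect of 0.4 SD and no drift, the same formula gives power 0.792. Opposite drift of 0.1 SD leaves a net 0.4 − 0.1 = 0.3 SD, with power 0.548. Opposite drift of 0.2 SD leaves 0.2 SD, with power 0.284.

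**What a pre-dose stability check could show.** If each of 50 patients had repeated recordings before the dose, the 95% confidence interval for the mean pre-dose change would have half-width t(0.975, 49)/√50 = 0.284 SD of that change. A drift of 0.2 SD would be detected with probability 0.284. Such a check can reveal large drift. It cannot rule out small drift.

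**The case against.** The sentence sits in a short summary written to explain the timing. It can be read as contrasting drug with surgery, and 1.b, directly below it, states the matter correctly. It is not an analysis rule. The definition of baseline, the number of recordings and the end of the primary window may be in an analysis plan that is not shown. All the drift values are assumed. An abrupt change locked in time to the infusion would be suggestive evidence of a drug effect.

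Much of this stands. The silence on baseline and thresholds is not a fault, and the drift figures do not show that drift matters in this setting. But an analysis plan could not make the word *only* true. A threshold can screen out small changes but does not say what caused the larger ones, and a plan written later cannot supply a comparison that the described design does not collect. Nor is the causal claim confined to the summary: the endpoint in 2.g is worded causally too.

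Three stronger readings are tempting and should not be drawn.

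- A reader might infer that the protocol contradicts itself on when the drug is given, because 1.a says before incision, 2.a says "after general anesthesia has been induced" and 2.g says "a single dose of fosaprepitant at the start of surgery". One dose can satisfy all three. Sections 2.a and 2.g are merely less specific.
- A reader might take the statement in 3.a that "the sensory and motor pathways are monitored throughout the surgical procedure" as defining this study's observation period. It is general background on monitored surgery. The point about later readings rests on 2.a alone.
- A reader might infer that the trial needs a control group. It needs one only to keep the causal claim, and a comparator would have to be squared with the statement in 2.e that "No standard treatment is being withheld".

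**Conclusion.** The concern holds and should be fixed. The attribution sentence in 1.a is wrong as written, and the causal endpoint in 2.g leans on it. The trial can describe and quantify how signals change after the dose. It cannot by itself establish that the drug was the cause.

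The size is unknown. Under the assumed paired test with 50 patients and no drug effect, false positives rise from 5% with no drift to 11%, 28% and 55% at drifts of 0.1, 0.2 and 0.3 SD. These are illustrations, not estimates for this trial. If drift and variability are negligible, the fault is one of wording only.

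The conclusion rests on one inference: that there is no comparator. The protocol never calls the study single-arm, but the procedures describe only dosed patients.

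**What to change.** 1. In 1.a, replace the attribution clause with wording such as *changes seen before incision are unlikely to be due to surgical injury*. This is the strength that 1.b supports. Word the endpoint in 2.g, and the conclusion drawn from it, as change in signals following the dose. State that an uncontrolled before/after design cannot by itself establish the drug as the cause.
2. Base the attribution on readings before incision and report later readings separately. Let 2.a and 2.g repeat the pre-incision condition that 1.a already states. This makes the three sections equally specific and changes no clinical instruction.
3. Optional, where the existing pre-incision period allows: report the change between repeated pre-dose recordings, with its 95% confidence interval, beside the change across dosing. Present it as a check on large drift, not as a correction.

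**Cost.** Item 1 is wording, and its price is a weaker causal claim. Item 2 is wording and reporting. Its downside is that an effect appearing only after incision falls outside the primary comparison, and the protocol gives no onset time by which to judge how likely that is. Item 3 needs a little more recording. The protocol does not give the time between induction and dosing, so its feasibility is not shown, and it does not remove bias from the main comparison.

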2. STUDY PROCEDURES

a. Procedures

On the day of surgery the patient will be consented in the preoperative area. We regularly use fosaprepitant in surgical patients undergoing procedures under general anesthesia with intraoperative neuromonitoring.

The patient will receive a single dose of 150 mg intravenous fosaprepitant after general anesthesia has been induced as prepared by pharmacy. Intraoperative neuromonitoring signals will be monitored for any changes during and after the administration of fosaprepitant.

The patient's intraoperative anesthetic management will be that typically utilized for surgical procedures with intraoperative neuromonitoring.

b. Procedure Risks

Using fosaprepitant in the operating room is widely used in the United States and is generally considered safe. This study will no withhold medication used to treat post-operative nausea and vomiting, rather, it seeks to determine if utilizing this very safe and effective medication during surgical procedures under general anesthesia with intraoperative neuromonitoring will alter or change intraoperative neuromonitoring signals due to the mechanism of action of the drug.

c. Use of Deception in the Study

No deception will be used.

d. Use of Audio and Video Recordings

No audio or video will be recorded.

e. Alternative Procedures or Courses of Treatment

At this point the use of fosaprepitant during surgery is at the discretion of the anesthesiologist. The effect of this medication on intraoperative neuromonitoring signals in patients having surgery under general anesthesia is not understood. No standard treatment is being withheld.

f. Will it be possible to continue the more (most) appropriate therapy for the participant(s) after the conclusion of the study?

After surgery the primary surgery team is free to utilize any nausea and vomiting control scheme they would like to use.

g. Study Endpoint(s)

Our study endpoint is whether a single dose of fosaprepitant at the start of surgery in patients having surgery under general anesthesia with intraoperative neuromonitoring causes any change in intraoperative neuromonitoring signals, and to quantify any such changes.

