10. BENEFITS

This study seeks to determine if fosaprepitant alters intraoperative neuromonitoring signals during general anesthesia. If it is found that this medication does alter intraoperative

neuromonitoring signals, it would be helpful to avoid administration of this medication during parts of the surgical procedure where changes in the intraoperative neuromonitoring signals could be mistakenly attributed to the surgical procedure causing neurological damage.

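### Anesthetic adjustments around the dose are neither held nor logged, so the size of signal change sought in section 2.g may be biased in either direction and cannot be credited to fosaprepitant on timing alone

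*Protocol*

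**What the plan says.** Four statements in the protocol bear on this point.

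- **Background care (section 2.a).** The patient's "intraoperative anesthetic management will be that typically utilized for surgical procedures with intraoperative neuromonitoring". The section does not ask for a stable anesthetic around the dose or for a record of changes to it.
- **Measurement period (section 2.a).** "Intraoperative neuromonitoring signals will be monitored for any changes during and after the administration of fosaprepitant". No closing time is given, and incision is not named as the limit.
- **Endpoint (section 2.g).** The question is whether one dose "causes any change in intraoperative neuromonitoring signals, and to quantify any such changes". This has a yes/no part and a size part, and no direction is specified.
- **Attribution (section 1.a).** Because the drug is given between induction and incision, "if there are any changes on the intraoperative neuromonitoring signals they can only be attributed to fosaprepitant".

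Every participant receives the drug (section 2.a: "The patient will receive a single dose of 150 mg intravenous fosaprepitant after general anesthesia has been induced"). No control group is described. Planned enrollment is 50 (section 8.a).

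**The concern.** With no control group, each patient's own signal before the dose is the only available comparison. Anything else that moves the signal between the two readings enters the estimate. Section 2.a leaves anesthetic management free to vary over that interval and asks for no record of it.

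This matters in two ways. An adjustment made in response to a signal change acts on the outcome itself and may undo part of what the trial is trying to measure. An adjustment made for another reason may shift the signal when the drug has done nothing. A pre-dose baseline alone does not separate these, because the later reading then reflects the drug and the adjustment together. Masking the reader does not help either, since the recorded signal has itself changed.

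The result is meant to guide when anesthesiologists give the drug. Section 10 worries that "changes in the intraoperative neuromonitoring signals could be mistakenly attributed to the surgical procedure causing neurological damage". A size that is too small would reassure wrongly. A size that is too large, or an effect that is not there, would restrict timing for no reason.

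**Working it through.** **1. Does dosing before incision support the attribution claim?** Set sections 1.a and 2.a side by side.

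- Dosing before incision excludes surgery as a cause, but only for readings taken before incision. Section 2.a sets no such limit.
- It does not exclude changes in anesthetic delivery, vasoactive drugs or neuromuscular blockade at any time, and section 2.a leaves anesthetic management open.
- Changes of stimulus setting or electrode belong to monitoring technique, which the protocol does not address. They too would make readings before and after the dose non-comparable.

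The exclusive attribution therefore does not follow from the timing.

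**2. Which part of the endpoint is exposed to masking?** A correction prompted by a fall requires that the fall was seen. That fall already meets the yes/no part of section 2.g. The size part is attenuated if it rests on a late or averaged reading, and is not attenuated if it rests on the largest change before any correction. The protocol specifies none of these.

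**3. Size of masking (illustration).** The protocol has no figure to reproduce: it gives 50 participants without a significance level, power, effect size or SD. Assume a true fall of 30%, a fraction f of patients whose signal is corrected fully to baseline, and a fraction r of their post-dose readings taken after correction. If all post-dose readings are averaged:

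observed fall = 30% × (1 − f × r)

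| f | r | Calculation | Observed fall |
|---|---|---|---|
| 0.25 | 0.25 | 30% × 0.9375 | 28.1% |
| 0.50 | 0.50 | 30% × 0.75 | 22.5% |
| 0.75 | 0.75 | 30% × 0.4375 | 13.1% |
| 0.50 | 1 (only a corrected reading used) | 30% × 0.5 | 15% |

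**4. Effect on a test of the mean change (illustration).** Assume a within-patient z-test with n = 50 and two-sided 5% significance. The effect detectable with 80% power is d = (1.960 + 0.842)/√50 = 0.396 SD. If a share m of the effect is masked, power = Φ(d(1 − m)√50 − 1.960):

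| m | Power |
|---|---|
| 0 | 80% |
| 0.05 | 75.9% |
| 0.10 | 71.3% |
| 0.25 | 55.6% |
| 0.50 | 28.8% |

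**5. The other direction (illustration).** With no drug effect and a mean shift of b SD from unrelated adjustments, the false-positive rate is Φ(b√50 − 1.960) + Φ(−b√50 − 1.960). At b = 0.1 this is 10.9%, and at b = 0.2 it is 29.3%, against a nominal 5%. With a true effect of 0.396 SD, a 0.1 SD shift in the same direction raises power from 80% to 93.9%. A 0.1 SD shift in the opposite direction lowers it to 55.4%.

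The documents fix none of m, f, r or b, so the net direction is undetermined.

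**The case against.** A reader might infer something stronger: that staff will correct falling signals, that the corrections will restore them, and that the trial will therefore understate or miss a real effect. The documents do not support that. Nowhere do they say that the anesthetic is adjusted when a signal falls, how often this happens or whether it works. Section 1.b says that signal changes at the beginning of surgery are unlikely to mean surgical damage, which if anything weakens the case for frequent correction then. Nor does the protocol say that all readings count equally, and a fall that prompts a correction has already been observed. These objections stand, and they are why the point is worded as a possibility with no fixed direction.

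It can also be said that the choice and summary of repeated readings belong in a statistical analysis plan, which is not at hand. That is fair for the summary rule. It does not cover the log: whether the time and reason of each adjustment are captured is a matter of study conduct, and an analysis plan cannot recover a reason that was never recorded. The attribution claim in section 1.a is also the protocol's own.

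Finally, stopping each patient's data at the first adjustment may end observation before the peak effect, and perhaps more often in strongly affected patients. This stands, and the fix allows for it.

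**Conclusion.** The point holds in a limited form. Usual-practice anesthetic management, unrecorded, over a period with no stated end means that the size of change in section 2.g may mix the drug's effect with that of adjustments. The bias may go either way. The yes/no part is less exposed to masking, but it remains open to changes produced by unrelated adjustments. The exclusive attribution in section 1.a is not justified by pre-incision timing alone.

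The documents do not show that the trial will miss an effect, or that the bias runs towards no change. The size cannot be established from them either. The 30% fall, f, r, m, b, the z-test and the significance level are all assumptions, and the masking table also assumes full restoration and a uniform effect. The figures show only that modest adjustments could matter with 50 patients. The point merits an amendment because the remedy is cheap and the log cannot be rebuilt reliably afterwards.

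**What to change.** Leave patient care as it is and change what is recorded and which readings carry the main result.

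- **Section 2.a:** from the last pre-dose reading to incision, log the time and reason of every change in anesthetic delivery, vasoactive drug, neuromuscular blocker, stimulus setting or electrode, noting whether a signal change prompted it.
- **Section 2.g:** base the main quantified change on the pre-dose reading against post-dose readings taken before incision, at the same stimulus settings, and before any adjustment that was triggered by a signal or is relevant to it. State in advance which adjustments count as relevant.
- **Sensitivity analysis:** report all pre-incision readings, including those after an adjustment, because stopping at the first one may come before the peak effect.
- **Section 1.a:** limit the attribution statement to pre-incision changes not accompanied by a logged adjustment.

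The cost is a short amendment and a few time-stamped entries, with no extra patients or procedures and no restriction on care. The downside is fewer usable readings, and possible informative truncation, in patients adjusted early.
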